### **7.3.1 Primary endpoint analyses**

#### Primary analyses

Descriptive statistics for the primary endpoint TSF will be presented.

The statistical model used for the analysis of the primary endpoint will be an analysis of variance (ANOVA) model on the logarithmic scale for each treatment relative to placebo. That is, the TSF will be log-transformed (natural logarithm) prior to fitting the ANOVA

Proprietary confidential information © 2020 Boehringer Ingelheim International GmbH or one or more of its affiliated companies

model. This model will include the fixed effect treatment (T1 and T2: treatment group, R: placebo, C: Phenelzine). The model is described by the following equation:

$$y_k = \mu + \tau_k + e_k, \text{ where}$$

$y_k$  = logarithm of response measured on treatment k,

$\mu$  = the overall mean,

$\tau_k$  = the  $k^{\text{th}}$  treatment effect,  $k = 1, 2, \dots$ ,

$e_k$  = the random error term,

where  $e_k \sim N(0, \sigma^2)$  i.i.d..

Point estimates for the ratios of the geometric means (T1/R), (T2/R) and (C/R) and corresponding two-sided 90% confidence intervals (CIs) will be provided.

For TSF the difference between the expected means for log(test)-log(reference) will be estimated by the difference in the corresponding adjusted means (Least Squares Means). Additionally their two-sided 90% confidence intervals will be calculated based on the residual error from the ANOVA and quantiles from the t-distribution. These quantities will then be back-transformed to the original scale to provide the point estimate and 90% CIs for each endpoint.

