3. If several actions are indicated at the same time, the intake of meals will be the last action.
4. At the end of trial visit the EoTrial examination includes physical examination, body weight, vital signs, ECG, safety laboratory (including pregnancy test in females), recording of AEs and concomitant therapies.
5. Only drug and alcohol screening in urine will be done at this time.
6. AEs and concomitant therapies will be recorded throughout the trial, but will be specifically asked for at the times indicated in the [Flow Chart](#) above.
7. From Day -11 to Day -2 escalating oral doses of tyramine from 10 to 700 mg /day will be administered. Baseline blood pressure prior to tyramine dosing defined as three consecutive measurements with a maximum range of 10 mmHg or, if a stable SBP will not be obtained within the 35 minutes, the mean of all 7 readings. Blood pressure monitoring continues 5 minutes after tyramine administration and approximately every 5 minutes thereafter for at least 2 hours and then approximately every 15 minutes for an additional 2 hours. Tyramine dose escalation is to be terminated when the predefined target elevation in SBP is reached (i.e., SBP increased  $\geq$ 30 mmHg from baseline for three consecutive measurements). Participants who do not attain the predefined target elevation in SBP within 4 hours after the maximum tyramine dose (700 mg) on Day -2 or TYR30 is  $<$  200 mg are screening failures. All other participants are going to be included in the study.
8. From Day 29 to Day 39 escalating oral doses of tyramine from 5 to 700 mg /day will be administered in Dose Groups 1 and 2 (concomitantly with BI 1467335 or placebo). The treatment is to be terminated once the participant reaches the predefined target elevation in SBP (i.e., SBP increased  $\geq$ 30 mmHg from baseline for 3 consecutive measurements), and then the participant is allowed for discharge after an overnight stay at trial site.
9. On Days 2 to 6, 8 to 13, 15 to 20 and 22 to 25, subjects are allowed to take their study medication at home if deemed appropriate by the investigator. Compliance of medication intake will be monitored by subject diary and daily phone contact (e.g. text message) between subject and site. The scheduled time for drug intake throughout the study for subjects assigned to Dose Group 1 and 2 (BI 1467335 or placebo) is 08:00 (applies for intake at home and at the trial site).

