### 6.2 DETAILS OF TRIAL PROCEDURES AT SELECTED VISITS

#### 6.2.1 Screening period

After having been informed about the trial, all subjects will provide written informed consent in accordance with GCP and local legislation prior to enrolment in the study.

For information regarding laboratory tests (including drug and virus screening), ECG, vital signs, and physical examination, refer to [Sections 5.2.3 to 5.2.6](#). For the tyramine challenge (Visit 2, hospitalisation from Day -12 up to Day -2; see Flowchart), results of this test are mandatory for final inclusion.

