## 7. STATISTICAL METHODS AND DETERMINATION OF SAMPLE SIZE

### 7.1 STATISTICAL DESIGN – MODEL

The main objective of this trial is to compare the primary endpoint tyramine sensitivity factor (ratio of TYR30 at steady state compared to TYR30 at baseline) as listed in [Section 2.1.2](#) between the different treatment arms (BI 1467335 10mg, 15mg, Placebo and Phenelzine).

The trial will be evaluated statistically by use of a linear model for the logarithmically transformed endpoint.

The assessment of safety and tolerability is a further objective of this trial, and will be evaluated by descriptive statistics for the parameters specified in [Section 2.2.2.2](#).

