## **7.7 DETERMINATION OF SAMPLE SIZE**

It is planned to enter a total of 62 subjects in the trial, because this sample size is considered sufficient to achieve the aims of this exploratory trial. With this sample size, the following precision in estimating the ratio of geometric means (test/reference) can be expected with 95% probability. Precision is defined as the ratio of upper CI limit to the relative BA estimate. Note that the precision is independent of the actual ratio of geometric means.

The observed coefficient of variation (gCV) for phenelzine [[R18-2841](#)] was roughly 86% for the tyramine sensitivity factor.

For various assumptions around the gCV of 86%, [Table 7.7: 1](#) provides an overview of the achievable precision for estimating the ratio of geometric means (test/reference). For illustrative purposes, the expected 90% confidence intervals are displayed for different values of the ratios T/R of geometric means.

Proprietary confidential information © 2020 Boehringer Ingelheim International GmbH or one or more of its affiliated companies

Table 7.7: 1

Precision that can be expected with 95% probability and illustrative two-sided 90% confidence intervals around the ratios of geometric means (T/R) for different ( $N=32$ )

gCV [%]	Precision upper CL / relative BA estimate	Ratio [%] *	Lower CL [%]	Upper CL [%]
80.0	1.67	100	60.06	166.50
80.0	1.67	150	90.09	249.75
80.0	1.67	175	105.11	291.37
80.0	1.67	200	120.12	333.00
80.0	1.67	600	360.36	998.99
86.0	1.72	100	58.31	171.49
86.0	1.72	150	87.47	257.23
86.0	1.72	175	102.05	300.10
86.0	1.72	200	116.63	342.98
86.0	1.72	600	349.88	1028.93

\*Ratio of geometric means (test/reference) for a PK endpoint is defined by  $\exp(\mu_T)/\exp(\mu_R)$ .

The expected 90% confidence interval limits in the table were derived by

$$\text{CI limit}_{\text{upper},\text{lower}} = \exp(\ln(\theta) \pm \omega),$$

with  $\theta$  being the ratio (T/R) on original scale and  $\omega$  the distance from the estimate  $\theta$  to either confidence interval limit on the log-scale, which was obtained from the achievable precision on the original scale.

The calculation was performed as described by Julius [R11-5230] using R Version 3.5.1.

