## **7.4 PRIMARY ENDPOINTS**

### **7.4.1 Primary analysis of the primary endpoint**

Primary analysis of the primary endpoint will be performed as defined in Sections 7.3.1 of the CTP.

The statistical model for the primary analysis defined in the CTP is an analysis of variance (ANOVA) model on the logarithmic scale including "treatment" as fixed effect. The model will include all three treatments at the same time, i.e., including data from treatments T1, C and R in the same analysis. The difference in TSF will be estimated by the ratios of the geometric means of

- 10 mg BI 1467335 (T1)/ Placebo (R)
- Phenelzine (C)/ Placebo (R)

of the primary endpoint.

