### **7.4.2 Sensitivity analysis, subgroup analysis, exploratory analysis of the primary endpoint**

The primary endpoint will also be assessed descriptively. Summary statistics, by treatment, will be presented for TSF, TYR30 at baseline and TYR30 at steady state.

[figure not shown]

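### The primary model for log TSF omits baseline TYR30, so T1/R is probably a little less precise than it could be and is open to chance baseline imbalance

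*Protocol*

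**What the plan says.** Protocol 7.1 defines the endpoint as the "tyramine sensitivity factor (ratio of TYR30 at steady state compared to TYR30 at baseline". Protocol 7.3.1 fits an ANOVA to its natural logarithm, with an overall mean, a treatment effect and an error: "This model will include the fixed effect treatment (T1 and T2: treatment group, R: placebo, C: Phenelzine". Two-sided 90% confidence intervals are given for each ratio to placebo.

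SAP 7.4.1 adds no term: "The model will include all three treatments at the same time, i.e., including data from treatments T1, C and R in the same analysis". SAP 7.4.2 uses the baseline value descriptively only: "Summary statistics, by treatment, will be presented for TSF, TYR30 at baseline and TYR30 at steady state". No visible section of either document enters baseline TYR30 as a covariate.

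The value exists for every included subject. Protocol 6.2.1 says of the baseline challenge that "results of this test are mandatory for final inclusion", and protocol 4.1.3 places allocation afterwards, on the morning of Day 1. Footnote 7 of the BI 1467335/placebo flow chart also selects on it. Screening failures are subjects who miss the target "elevation in SBP within 4 hours after the maximum tyramine dose (700 mg) on Day -2 or TYR30 is" below 200 mg.

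**The concern.** On the log scale TSF is a change score. Let b be the slope of log steady-state TYR30 on log baseline TYR30. A treatment-only model of the change sets b to 1 instead of estimating it, and that is efficient only if steady-state TYR30 follows baseline one for one.

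Three features of the design make b below 1 likely:

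- TYR30 is the first dose on a coarse ladder that meets the criterion, from a single escalation.
- Entry selects on that same noisy value, so some regression to the mean is expected.
- In Dose Groups 1 and 2 the repeat challenge starts on Day 29, about a month or more after the baseline challenge.

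If b is below 1, error in the baseline value stays in each TSF, and a chance difference in baseline TYR30 between arms passes partly into T1/R. This matters more than usual here. Protocol 7.2 sets no acceptance range, so the estimate and its interval are the result. SAP section 4 reports that no 15 mg subject has a TSF, so T1/R is the only BI 1467335 comparison left.

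**Working it through.** **Inputs from the documents.** The gCV of TSF "was roughly 86% for the tyramine sensitivity factor" (protocol 7.7, from a phenelzine group), so the log variance is ln(1 + 0.86²) = 0.5537 and the SD is 0.744. There are 16 active and 8 placebo subjects per BI dose group (protocol 3.1). The 90% CI is two-sided. Baseline TYR30 runs from 200 to 700 mg (BI/placebo flow chart).

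**Assumptions.** The slope b and the retest correlation ρ are not given. Baseline log SD is taken as 0.30–0.43; six equally frequent doses from 200 to 700 mg give 0.425. The number of placebo subjects with a TSF is not stated and could be 8 to 16, so 16 v 8 is the cautious case.

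**1. The plan's own figure.** Table 7.7: 1 uses 16 v 16 and 95% assurance:

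exp{t(0.95, 30) × 0.744 × √(1/16 + 1/16) × √(χ²(0.95, 30)/30)} = 1.715, or 58.31% to 171.49% around 100%.

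This matches the table (1.72), which assumes an unadjusted comparison and is not in error.

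**2. Unadjusted, 16 v 8.** The upper-limit factor, without the assurance term and so not comparable with 1.72, is exp{t(0.95, 22) × 0.744 × √(1/16 + 1/8)} = exp(1.717 × 0.744 × 0.433) = 1.739. With 14 phenelzine subjects in the same model (35 df) it is 1.724.

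**3. Adjusted, 16 v 8, gCV 86%.** The residual variance is 0.5537 − (1 − b)² × SD², where SD is the baseline log SD. It is multiplied by 1 + 1/20 for estimating the slope, with t(0.95, 21) = 1.721.

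| b | baseline SD 0.30 | baseline SD 0.43 |
|---|---|---|
| 0.25 | 1.72 | 1.67 |
| 0.50 | 1.74 | 1.72 |
| 0.75 | 1.76 | 1.75 |

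Against 1.74 unadjusted, break-even needs (1 − b)² × SD² = 0.5537 × {1 − (1.717/1.721)²/1.05} ≈ 0.0286. That gives b ≈ 0.44 (SD 0.30) or 0.61 (SD 0.43). At b = 1 the factor is 1.765, and ln 1.765 / ln 1.739 ≈ 1.027, so the worst cost is a half-width about 3% wider.

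**4. Simulation on the protocol's ladder.** Normal log thresholds were read up to the next dose, with 200–700 mg entry, no drug effect, and steady-state values beyond the ladder set to 700 mg. For 16 v 8 the SE of log T1/R fell by about 2–11% at slopes 0.42–0.79 and was unchanged at 0.91. For 16 v 16 the adjusted-to-unadjusted variance ratio was 0.94 at slope 0.81, 0.86 at 0.65, 0.78 at 0.42, 0.75 at 0.44 and 0.63 at 0.17. The 16 v 16 runs had log TSF SDs of 0.21–0.45, well below 0.744, which is why these gains exceed those in step 3.

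**5. Chance imbalance, 16 v 8.** The SE of the difference in mean log baseline is 0.433 × 0.30 = 0.130 to 0.433 × 0.43 = 0.186, a 14–20% difference in baseline TYR30. At b = 0.5, half passes through on the log scale: exp(0.065) = 1.07 to exp(0.093) = 1.10. For scale, the SE of log T1/R at gCV 86% is 0.744 × 0.433 = 0.322, so the shift is about 0.2 to 0.3 of one SE.

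**6. Same estimand.** With S and B for log steady-state and baseline TYR30, S − B = μ + τ + βB + e rearranges to S = μ + τ + (1 + β)B + e. The treatment contrast τ is the same in both, so TSF stays the endpoint. Writing the ratio the other way up changes only the sign.

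**The case against.** The strongest reply is that nothing is broken. T1/R is a randomised comparison, its interval already allows for chance imbalance, TSF already uses each subject's baseline, and SAP 7.4.2 tabulates baseline TYR30 by arm, so an imbalance would be visible. All of this stands. A reader might infer from the missing covariate that T1/R is biased or that Table 7.7: 1 is wrong. The documents support neither reading: the estimate is valid on average over randomisation, and the table reproduces.

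The second reply concerns size. A reader might apply the usual equal-variance formula, Var(adjusted)/Var(unadjusted) = (1 + ρ)/2, and expect variance to fall by 35–15% for ρ of 0.3–0.7. At gCV 86% that formula needs a baseline log SD of 0.744/√(2(1 − ρ)), which is 0.63, 0.74 and 0.96 at ρ = 0.3, 0.5 and 0.7. No distribution on 200–700 mg can exceed ln(3.5)/2 = 0.626. A large saving in subjects therefore cannot be claimed on the plan's own figures.

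The third reply concerns how the covariate would be used. In the three-arm model the common slope would come partly from phenelzine. That group is open-label and not randomised (protocol 7.6), has an extra 150 mg step at steady state (protocol 5.6.1), and its flow chart has no 200 mg floor. Sponsor functions, including the statistician, are unblinded (protocol 4.1.5), and the SAP is dated after the decision to stop. Replacing the protocol's model at that stage would invite the charge of a choice made with data in view. This limits the form of the remedy but does not remove the case for one.

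**Conclusion.** The point holds as a modest refinement. Both documents leave out a covariate that is measured before allocation, is complete, and would probably predict TSF. The likely cost is some lost precision: about 2–11% in the SE of log T1/R for slopes of about 0.4–0.8, and nothing near 0.9. At gCV 86% with baseline log SD 0.30–0.43 there is little to gain unless the slope is below about 0.5. The firmer benefit is protection against a chance imbalance, where 1 SE moves unadjusted T1/R by about 7–10% at slope 0.5 with 16 v 8.

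These sizes rest on an assumed slope, baseline spread and placebo count. They also rest on a gCV taken from phenelzine, which may not describe the placebo and BI arms. The 200 mg floor appears only in the BI/placebo flow chart; if it was not applied, baseline spread and the gain could both be larger.

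**What to change.** In SAP 7.4.1, specify in writing before the data are analysed:

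- An ANCOVA of log TSF on treatment plus centred log(baseline TYR30).
- For T1/R, a slope estimated from the randomised BI 1467335 and placebo subjects; or a check of the common slope before phenelzine is included.
- Adjusted T1/R with its 90% CI, reported next to the protocol's treatment-only ratio. Both should be shown whatever they give, because sponsor functions are unblinded.
- A statement that adjusted C/R is read cautiously, because phenelzine is not randomised and adjustment cannot remove all confounding.
- The number of placebo subjects with a TSF.

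The cost is a few SAP sentences, one residual degree of freedom, and a linear, common-slope assumption. No new data are needed. The covariate does not deal with subjects who fail to reach TYR30 at 700 mg at steady state; that censoring needs its own rule.

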### 7.3.2 Secondary endpoint analyses

Not applicable, the study does not evaluate secondary endpoints.

### 7.3.4 Safety analyses

Safety will be analysed based on the assessments described in [Section 2.2.2.2](#). All treated subjects (TS, refer to [Section 7.2](#)) will be included in the safety analysis. Safety analyses will be descriptive in nature and based on BI standards. No hypothesis testing is planned.

For all analyses, the treatment actually administered (= treatment at onset) to the subject will be used (any deviations from the randomised treatment will be discussed in the minutes of the Report Planning Meeting).

Treatments will be compared in a descriptive way. Tabulations of frequencies/proportions will be used to evaluate categorical (qualitative) data, and tabulations of descriptive statistics will be used to analyse continuous (quantitative) data.

Proprietary confidential information © 2020 Boehringer Ingelheim International GmbH or one or more of its affiliated companies

Measurements (such as ECG, vital signs, or laboratory parameters) or AEs will be assigned to treatments (see [Section 4.1](#)) based on the actual treatment at the planned time of the measurement or on the recorded time of AE onset (concept of treatment emergent AEs). Therefore, measurements planned or AEs recorded prior to first intake of trial medication will be assigned to the screening period, those between first trial medication intake and end of REP (see [Section 1.2.4](#)) will be assigned to the treatment period. Events occurring after the REP but prior to next intake or end of trial termination date will be assigned to 'follow-up'. In case of two or more treatments, the follow-up will be summarized according to the previous treatment. These assignments including the corresponding time intervals will be defined in detail in the TSAP. Note that AEs occurring after the last per protocol contact but entered before final database lock will be reported to Pharmacovigilance only and will not be captured in the trial database.

Additionally, further treatment intervals (analysing treatments) may be defined in the TSAP in order to provide summary statistics for time intervals, such as combined treatments, on-treatment totals, or periods without treatment effects (such as screening and follow-up intervals).

Adverse events will be coded using the Medical Dictionary for Regulatory Activities (MedDRA). Frequency, severity, and causal relationship of AEs will be tabulated by treatment, system organ class, and preferred term. SAEs, AESIs (see [Section 5.2.6.1](#)), and other significant AEs (according to ICH E3) will be listed separately.

Previous and concomitant therapies will be presented per treatment group without consideration of time intervals and treatment periods.

Laboratory data will be compared to their reference ranges. Values outside the reference range as well as values defined as possibly clinically significant will be highlighted in the listings. Additionally, differences from baseline will be evaluated.

Vital signs or other safety-relevant data will be assessed with regard to possible on-treatment changes from baseline.

Relevant ECG findings will be reported as AEs.

## **7.4 INTERIM ANALYSES**

No interim analysis is planned. However, an informal exploratory analysis of TSF in the open label phenelzine group may be conducted if considered necessary.

## **7.5 HANDLING OF MISSING DATA**

### **7.5.1 Safety**

It is not planned to impute missing values for safety parameters.

## **7.6 RANDOMISATION**

Subjects within BI 1467335 dose groups (including Placebo) will be randomised stratified by gender to one of the 3 treatment arms in a 1:1:1 ratio. Subjects within the phenelzine treatment group (positive control without placebo control) will not be randomised. The block size will be documented in the CTR.

The sponsor will arrange for the randomisation as well as packaging and labelling of trial medication. The randomisation list will be generated using a validated system that uses a pseudo-random number generator and a supplied seed number so that the resulting allocation is both reproducible and non-predictable.

The randomisation list will contain additional blocks to allow for subject replacement (refer to [Section 3.3.5](#)).

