Number of subjects total entered each treatment	62 Dose Group 1 (BI 1467335 - 10 mg): 24 subjects (16 active + 8 placebo); Dose Group 2 (BI 1467335 - 15 mg): 24 subjects (16 active + 8 placebo); Dose Group 3 (phenelzine - 30 mg): 14 subjects (all active).
Diagnosis	Not applicable
Main criteria for inclusion	Healthy male/female subjects, age of 18 to 45 years (inclusive), body mass index (BMI) of 18.5 to 29.9 kg/m  (inclusive); at least 30% of each gender to be included into each Dose Group
Test product dose mode of admin.	BI 1467335, film-coated tablets, 5 mg of free base 10 mg (2 x 5 mg) QD and 15 mg (3 x 5 mg) QD Oral with 240 mL of water
Reference product dose mode of admin.	Matching placebo to BI 1467335 Not applicable Oral with 240 mL of water
Comparator dose mode of admin.	Phenelzine (Nardil ® ), tablets, 15 mg 15 mg BID Oral with 240 mL of water

Proprietary confidential information © 2020 Boehringer Ingelheim International GmbH or one or more of its affiliated companies

Challenge agent	Tyramine powder in capsules
dose	Baseline (Day -10 to Day -1, tyramine powder alone; each subject receives escalating doses, dose escalation to be stopped as soon as TYR30 has been obtained): 10, 25, 50, 100, 200, 300, 400, 500, 600, and 700 mg QD.  At steady state (for BI 1467335 dose groups Day 29 up to Day 39 , for phenelzine dose group Day 8 to Day 19, tyramine powder in combination with assigned study treatment; tyramine dose escalation to be stopped as soon as TYR30 has been obtained): 5, 10, 25, 50, 100, 200, 300, 400, 500, 600, and 700 mg QD An intermediate dose of 150 mg QD only in phenelzine group.
mode of admin.	Oral with 240 mL of water

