### 3. DESCRIPTION OF DESIGN AND TRIAL POPULATION

### 3.1 OVERALL TRIAL DESIGN AND PLAN

In total, 62 healthy male and female subjects are planned to participate in this multiple dose study.

The primary outcome of the study will be the tyramine sensitivity factor (TSF), which is defined as the ratio of the tyramine dose causing an increase in systolic blood pressure (SBP)  $\geq 30$  mmHg for at least 3 consecutive measurements (TYR30) at baseline and following a treatment of 28 days with BI 1467335 or placebo QD, or 7 days with phenelzine BID. A treatment duration of 28 days is required for BI 1467335 to reach steady state, whereas 7 days is considered sufficient for phenelzine.

As part of the screening procedure subjects will be challenged with escalating oral doses of tyramine. Tyramine doses will be escalated from 10 mg to 700 mg QD (25, 50, 100, 200, 300, 400, 500, 600, 700 mg) on a daily basis. For each subject, the tyramine dose escalation will be stopped when an increase of systolic blood pressure (SBP)  $\geq 30$  mmHg for at least 3 consecutive measurements is measured (i.e. TYR30). Participants who will not attain the predefined target elevation in SBP within 4 hours after the highest tyramine dose (700 mg) will not be included in the study.

Subjects considered eligible to enter the study will be assigned to one of three dose groups. The three dose groups to be evaluated are outlined in [Table 3.1: 1](#).

Table 3.1: 1 Dose groups

Dose Group	1	2	3
	BI 1467335	BI 1467335	Phenelzine (Nardil®)
Daily dose (mg)	10	15	30
Posology	1-0-0	1-0-0	1-0-1
Treatment duration	Up to Day 39	Up to Day 39	Up to Day 19
Number of subjects	24	24	14
Subjects receiving placebo	8	8	0
Subjects receiving active drug	16	16	14

Dose Group 1 and 2 consists of 24 subjects each, with 16 subjects per dose group assigned to BI 1467335 (active drug) and 8 subjects assigned to placebo. Both BI 1467335 dose groups will be conducted according to a double-blind, randomised, multiple-dose, placebo-controlled within dose groups, parallel group design.

Dose Group 3 will be conducted open-label with no placebo control, and consists of 14 subjects receiving the same treatment of phenelzine as positive control (comparator).

Proprietary confidential information © 2020 Boehringer Ingelheim International GmbH or one or more of its affiliated companies

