### **3.2 DISCUSSION OF TRIAL DESIGN, INCLUDING THE CHOICE OF CONTROL GROUP**

In both BI 1467335 dose groups, double-blind conditions regarding the subject's treatment (active drug or placebo) are maintained within each dose group. Although the current dose level will be known to subjects and investigators, the risk of an observer bias with regard to dose dependent effects and the primary endpoint (TSF) is considered low. The use of placebo will allow estimating the impact of individual factors on the results of the tyramine challenge.

Phenelzine as an unselective MAO-inhibitor was consistently shown to increase TSF [[R18-2841](#)] and phenelzine was therefore selected as positive control. Because of the expected pronounced effect on TSF a reliable blinding of the phenelzine treatment is considered not applicable, and therefore this dose group will be conducted open label. The anticipated effects on TSF in the phenelzine treatment group will serve as a benchmark to conclude about effects on TSF in the BI 1467335 dose groups. As a validation of study conduct, the study will start with subjects of the phenelzine group, before subjects of the BI 1467335 dose groups may enter the study.

Dosing duration for BI 1467335 and phenelzine is considered sufficient to achieve steady-state drug exposure and to exclude transient effects.

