**The characteristics of the reference product (placebo) is given below:**

#### **Reference**

Substance: Placebo matching in size and weight to 5 mg tablet

Pharmaceutical formulation: Film-coated tablet

Source: Boehringer Ingelheim Pharma GmbH & Co. KG, Germany

Unit strength: n.a.

Posology: 2-0-0 / 3-0-0

Route of administration: oral

Duration of use: up to 39 days

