### **Assessment of COVID-19 Impact**

Due to the study interruption caused by the Covid-19 pandemic the decision was made to stop the study prematurely. This decision was based on the fact that the data from the 10 mg BI group was thought to be sufficient to adequately address the main study objective.

The study was permanently discontinued while the 15mg BI 1467335 group was still ongoing, due to lock down of the site. None of the subjects in the 15mg BI 1467335 group completed the tyramine challenge at visit 3. Therefore, TYR30 at steady state and the primary endpoint TSF are not available for the 15mg BI 1467335 group. As a consequence, the ratio of 15mg BI 1467335 (T2)/Placebo (R) (primary analysis of primary endpoint) can not be calculated. For safety evaluation all data will be used.

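### Protocol Section 7.6 describes one 1:1:1 randomisation to three arms, which conflicts with the 2:1 design within dose groups of known dose; the placebo set behind T1/R is not defined, and the stratification factor sex is missing from the ANOVA

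*Protocol*

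**What the plan says.** **Allocation.** Protocol Section 7.6 states that subjects in the BI 1467335 dose groups, placebo included, are "randomised stratified by gender to one of the 3 treatment arms in a 1:1:1 ratio". The synopsis gives a different structure, "Dose Group 1 (BI 1467335 - 10 mg): 24 subjects (16 active + 8 placebo"), with the same split for 15 mg. Section 3.1 repeats it: "with 16 subjects per dose group assigned to BI 1467335 (active drug) and 8 subjects assigned to placebo".

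**Blinding.** Section 3.2 says "double-blind conditions regarding the subject's treatment (active drug or placebo) are maintained within each dose group", and concedes an open dose level: "Although the current dose level will be known to subjects and investigators". Section 4.1.1 lists two placebo regimens ("Posology: 2-0-0 / 3-0-0"), one for each tablet count.

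**Timing.** Under Section 3.1, all dose groups may enter once at least 8 phenelzine subjects have completed. No order is set for the 10 mg and 15 mg groups, and nothing says how a subject reaches one or the other. SAP Section 4 (Assessment of COVID-19 Impact) reports: "The study was permanently discontinued while the 15mg BI 1467335 group was still ongoing". No subject in that group completed the steady-state challenge, while the 10 mg data were thought sufficient.

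**Model.** Protocol Section 7.3.1 says "This model will include the fixed effect treatment" and names no other term. SAP 7.4.1 keeps treatment as the only effect and puts T1, C and R in one ANOVA. It does not say which dose group the placebo subjects in R come from.

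**The concern.** A subject who enters a dose group of known dose can receive only that dose or placebo. A single draw over 10 mg, 15 mg and placebo therefore cannot be carried out in the design of Sections 3.1 and 3.2. The two descriptions also imply different randomised comparators. Under one three-arm list, every placebo subject is a concurrent control for 10 mg. Under 2:1 within dose groups, only the 8 placebo subjects of Dose Group 1 were randomised against 10 mg.

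While both groups were expected to finish, this was mainly a question of wording. After the early stop, T1/R is the only BI 1467335 comparison left. Whether R holds about 8 subjects or more, and whether any of them come from the other dose group, bears on both its precision and its interpretation.

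Separately, a factor used to stratify allocation would ordinarily appear in the model. If it is prognostic and left out, its variance stays in the residual.

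**Working it through.** **1. Totals.** 2:1 in two groups of 24 gives 16:8 and 16:8. Pooled, that is 16 (10 mg) : 16 (15 mg) : 16 (placebo), the same as 1:1:1 over 48. The conflict concerns the procedure and the comparator, not the counts.

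**2. The plan's own figure.** Inputs from Protocol Sections 7.2 and 7.7: two-sided 90% interval, 95% probability, gCV 86%, N = 32 (16 v 16). With s = sqrt(ln(1 + gCV²)) = 0.744,

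precision = exp[ t(0.95, df) × s × sqrt(χ²(0.95, df)/df) × sqrt(1/n1 + 1/n2) ].

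At df = 30: exp(1.697 × 0.744 × sqrt(43.77/30) × sqrt(2/16)) = exp(0.539) = 1.715. The limits at a ratio of 100% are 58.31 and 171.49, as printed in Table 7.7: 1, which shows the precision as 1.72. The gCV 80% rows reproduce too (1.665, printed as 1.67). The table therefore rests on placebo pooled over both dose groups.

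**3. If R is Dose Group 1 placebo only.** Assumption: all 16 active and 8 placebo subjects of Dose Group 1 provide a TSF; the documents give no completer counts. The standard error grows by sqrt(1/16 + 1/8) / sqrt(1/16 + 1/16) = 1.22. Three-arm df use 14 phenelzine subjects: 16+16+14−3 = 43 and 16+8+14−3 = 35.

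| gCV 86% | 16 v 16 | 16 v 8 |
|---|---|---|
| Two-arm | 1.72 (df 30) | 1.99 (df 22) |
| Three-arm | 1.68 (df 43) | 1.91 (df 35) |

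At a ratio of 100%, the two-arm interval goes from about 58-171% to 50-199%, and the three-arm interval from about 59-168% to 52-191%.

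**4. Is the SAP's account compatible with one concurrent list?** Under simple 1:1:1 allocation with similar follow-up, the chance that none of k completers is on 15 mg is (2/3)^k: 3.9% for k = 8 and 0.006% for k = 24 (k is assumed). Staggered groups are the likelier explanation. This speaks to timing; staggered groups would give the same pattern under any within-group ratio.

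**5. Sex in the model.** If sex explains a share R² of log-TSF variance, s is multiplied by sqrt(1 − R²) and one df is lost. No document gives R²; 0 to 20% is an assumed range. Change in log-scale interval width at gCV 86%, from the same formula:

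| R² | 16 v 16, df 30 to 29 | 16 v 8, df 22 to 21 | 16 v 8 with phenelzine, df 35 to 34 |
|---|---|---|---|
| 0 | +0.4% | +0.7% | +0.3% |
| 5% | −2.2% | −1.9% | −2.2% |
| 20% | −10.2% | −10.0% | −10.3% |

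For 16 v 16, precision goes from 1.715 to 1.719 at R² = 0 and to 1.623 at R² = 20%.

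**The case against.** **The ratio costs no precision.** A reader might infer that 7.6 promises 16 placebo subjects for T1/R while the design delivers 8. The documents do not support that. The protocol plans one pooled R, its table uses 16 v 16, and 1:1:1 may simply be the pooled ratio, loosely worded. The 16 v 8 figures come from restricting R, or from the early stop. This stands in full; what remains is that the stated procedure and the design disagree.

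**Sequential running is not shown.** The SAP gives no enrolment order or dates, and the protocol lets all groups enter together. Overlap is not excluded, so non-parallel running is an inference. Nor does a 1:1:1 list by itself mean a concealed dose, since tablet count reveals it under any list.

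**The placebo question may be moot.** The per-protocol set needs a primary endpoint. If the SAP's 15 mg group includes its placebo subjects, none of them has a TSF and R is already Dose Group 1 placebo. But SAP Section 6.1 lists Placebo as a treatment group separate from 15 mg, so the term is ambiguous. No error in R is demonstrated; a clarifying sentence is still needed.

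**Sex is optional.** TSF is a within-subject ratio, so sex differences in baseline sensitivity may largely cancel. Omission is conservative, the trial is aimed at estimation, and phenelzine was neither randomised nor stratified. The SAP is dated after the stop, with sponsor functions unblinded, so a new covariate needs justification. These points limit the expected gain. The justification is available, though: sex was the stratification factor fixed in the protocol.

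**Conclusion.** The inconsistency is real. Section 7.6 cannot be followed as written alongside the synopsis and Sections 3.1 and 3.2, and the documents do not say how subjects are assigned to Dose Group 1 or 2. It does not by itself alter the sample size of 62 or the planned precision of 1.72.

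The practical consequence is conditional. If R consists only of placebo subjects from the 10 mg dose group, and 16 v 8 complete, precision worsens from 1.72 to 1.99 (two-arm) or from 1.68 to 1.91 (three-arm with 14 phenelzine). If R also holds placebo subjects from the 15 mg group, the comparison may pool non-concurrent placebo without a dose-group term or a stated rule. The SAP does not settle which applies.

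Leaving sex out is the smaller part. It should not be read as biasing T1/R or invalidating its interval: the ratio normally stays unbiased, and the interval is conservative to the extent that sex is prognostic, which the documents do not establish.

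**What to change.** - **Protocol 7.6:** state 2:1 active to placebo within each dose group, stratified by sex, in agreement with Section 3.1, and say how subjects are assigned to Dose Group 1 or 2.
- **SAP 7.4.1:** state which placebo subjects form R and how many come from each dose group. Use placebo randomised in the 10 mg dose group as the reference for T1/R, or report that comparison as a sensitivity analysis if a pooled R is kept.
- **SAP 7.4.1 model:** add sex as a fixed effect, citing its role in the randomisation, and record the change in SAP Section 4. Showing the treatment-only result beside it would answer any question about a covariate added after the stop.

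The cost is wording, one model term and one residual degree of freedom. Restricting R to Dose Group 1 placebo gives up any Dose Group 2 placebo data that exist, which is the reason to allow it as a sensitivity analysis.
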